1.1.1 Expression of Objectives and Endpoint using the Estimand Framework

Primary endpoints and key secondary endpoints are expressed using the estimand framework in [Table 2](#), following the International Conference on Harmonization E9 (R1) statistical principles for clinical trials (ICH 2020).

Table 2 Objectives and Estimands

Primary Objective(s)	Estimand Definition

• To evaluate the efficacy of tiragolumab plus atezolizumab and CE compared with placebo plus atezolizumab and CE in patients with previously untreated ES-SCLC without presence or history of brain metastases at baseline	
• Population: Patients with previously untreated ES-SCLC without presence or history of brain metastases at baseline• Variable: Time from randomization to the first occurrence of the respective event of interest (as defined in Table 1).• Treatments:
○ Experimental: tiragolumab + atezolizumab + CE (induction phase; four 21-day cycles) followed by tiragolumab + atezolizumab (maintenance phase; 21-day cycles)○ Control: placebo + atezolizumab + CE (induction phase; four 21-day cycles) followed by placebo + atezolizumab (maintenance phase; 21-day cycles)• Intercurrent events:
○ Start of NPT prior to the respective event of interest○ Early discontinuation from study treatment for any reason prior to the respective event of interest• Handling of intercurrent events: A treatment-policy with regards to the intercurrent events listed above will be applied for the primary analysis• Summary measure: Hazard ratio for the respective variable

Table 2 Objectives and Estimands (cont.)

Selected Secondary Objective(s)	Estimand Definition

Evaluate the efficacy of tiragolumab plus atezolizumab and CE compared with placebo plus atezolizumab and CE	
The estimands for OS and PFS as secondary endpoints are defined similarly as for the primary endpoints except the following:
 
Population: Patients with previously untreated ES-SCLC 
The estimand for secondary endpoint of confirmed ORR is defined similarly as for the primary endpoints in terms of population and treatments; the other attributes are defined as follows:
 
Variable:
Whether patients achieved a confirmed objective response (i.e., CR or PR on two consecutive occasions ≥ 4 weeks apart), as determined by the investigator according to RECIST v1.1Intercurrent events:
Start of NPT prior to the variable of interest is observedEarly discontinuation from study treatment for any reason prior to the variable of interest is observedHandling of intercurrent events: A treatment-policy with regards to the intercurrent events listed above will be applied for the analysis of confirmed ORRSummary measure:
Difference in proportions

Table 2 Objectives and Estimands (cont.)


To evaluate the quality of life of patients treated with tiragolumab plus atezolizumab and CE compared with placebo plus atezolizumab and CE	
The estimand for secondary endpoint of TTCD is defined similarly as for the primary endpoints in terms of population and treatments; the other attributes are defined as follows:
 
Variable: Time from randomization until the first confirmed clinically meaningful deterioration on physical functioning and GHS/QoL using the EORTC QLQ-C30 select scales; confirmed clinically meaningful deterioration is defined as a clinically meaningful decrease from baseline that must be held for at least two consecutive assessments or an initial clinically meaningful decrease from baseline followed by death from any cause within 3 weeks.Intercurrent events:
Start of NPT prior to a confirmed clinical meaningful deteriorationEarly discontinuation from study treatment for any reason prior to a confirmed clinical meaningful deteriorationDeath that occurs before patients report any clinically meaningful deteriorationHandling of intercurrent events: A treatment policy strategy with regards to the start of NPT and early discontinuation; and while-on-treatment/while-alive strategy for death will be applied for the TTCD analysis.Summary measure: Hazard Ratio for TTCD
--	--

CE=carboplatin and etoposide; CR=complete response; ES-SCLC=extensive-stage small cell lung cancer; EORTC=European Organization for Research and Treatment of Cancer; GHS=global health status; NPT=non-protocol anti-cancer therapy; ORR=objective response rate; OS=overall survival; PFS=progression-free survival; PR=partial response; QLQ-C30=Quality-of-Life Questionnaire Core 30; TTCD=time to confirmed deterioration.

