6.4 EFFICACY ANALYSES

Unstratified analysis will be considered as primary results given the potential small sample size within each stratum. The stratified analysis will also be provided.

The stratification factors will be the same as the randomization stratification factors used for IxRS (ECOG Performance Status and LDH) and applied to all endpoints where stratification analyses are planned. Stratification factor(s) may be removed from the stratified analyses if there is risk of overstratification. Analyses based on stratification factors recorded on the eCRF will also be provided if considerable discrepancy is observed between IxRS and eCRF records.

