6.4.1 Co-Primary Efficacy Endpoints

The co-primary efficacy endpoints are PFS (as assessed by the investigator according to RECIST v1.1) and OS in the PAS.

PFS is defined as the time between the date of randomization and the date of first documented disease progression (as assessed by investigators according to RECIST v1.1) or death, whichever occurs first. Patients who have not experienced disease progression and have not died by the time of analysis will be censored at the time of the last tumor assessment. Patients with no post-baseline tumor assessment will be censored at the date of randomization.

OS is defined as the time between the date of randomization and death from any cause.

Data for patients who are not reported as having died by the date of analysis will be censored at the date when they were last known to be alive. Data for patients who do not have post-baseline information will be censored at the date of randomization.

PFS and OS will be compared between treatment arms with use of the unstratified log-rank test. The HR for PFS and OS will be estimated using both unstratified and stratified Cox proportional hazards model. The 95% CI for the HR will be provided.

[REDACTED]

The investigator-assessed PFS rates at 6 months and at 1 year and OS rates at 1 year, 18 months, and 2 years after randomization will be estimated using Kaplan-Meier methodology for each treatment arm, along with 95% CIs calculated using the standard error derived from Greenwood's formula. The 95% CI for the difference in PFS rates and OS rates between the two treatment arms will be estimated using the normal approximation method.

The timing of the final PFS analysis is described in Section 6.1.1 and the analysis timing for OS is described in Section 6.1.2.

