6.4.2.4 Patient-Reported Outcomes

TTCD in the PAS and the FAS for physical functioning and GHS using the EORTC QLQ-C30 is defined as the time from the date of randomization until the first confirmed clinically meaningful deterioration. Confirmed clinically meaningful deterioration for GHS and physical functioning is defined as a clinically meaningful decrease from baseline in GHS or physical functioning scale score that must be held for at least two consecutive assessments or an initial clinically meaningful decrease above baseline followed by death. A score change of ≥ 10 -point is considered to be clinically meaningful by patients for lung cancer-related symptoms, GHS and physical functioning subscale score (Osaba et al. 1998).

For TTCD, data for patients will be censored at the last time when they completed an assessment if they have not experienced a confirmed clinically meaningful deterioration event at the CCOD. If no baseline or post-baseline assessment is performed, patients will be censored at the randomization date. TTCD using the EORTC scale will be analyzed using the same methods as for PFS. Further details regarding the TTCD analyses for the EORTC measures will be described in the SAP.

Summary statistics (mean, SD, median, 25th and 75th percentiles, and range) and the mean change from baseline of linear-transformed scores will be reported for all of the items and subscales of the EORTC QLQ-C30 and EORTC IL46 (an item for troubled by side effects) questionnaires at each timepoint, the end of treatment, at the time of progression (per RECIST criteria), and at the time of clinical progression (if different from time to progression). In addition, mean scores for GHS, physical functioning, and selected symptom scales will be presented for the induction phase and the maintenance phase.

PRO-CTCAE data will be analyzed by treatment arm, the number (percentage) of patients reporting symptom by "frequency," "severity," "interference," and "presence" at each assessment. In addition, the frequency of symptoms will be cross tabulated with the severity of the symptom to explore the impact of the symptom when it occurred.

A summary table of the percentage of patients reporting severity of a symptom as 'severe' or 'very severe' over the course of the study by treatment arm will also be provided. Finally, a longitudinal analysis of change may be employed to understand how symptoms may have changed over the course of treatment.

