5.4.2.3 Time to Confirmed Deterioration in Physical Functioning and Global Health Status

Patient-reported physical functioning (items 1-5) and global health status (GHS)/ quality of life (QoL) (items 29-30) as collected and measured by the European Organization for the Research and Treatment of Cancer (EORTC) Quality of Life Questionnaire Core 30

(QLQ-C30). A high score for the physical function subscale represents a high/healthy level of functioning and a high score for the GHS/QoL subscale represents a high health related quality of life. Both scales will be linearly transformed so that each score will range from 0 to 100. A score change of at least 10-point in GHS/QoL and functional subscale score is perceived by patients as clinically meaningful (Osoba et al. 1998).

The estimand for time to confirmed deterioration (TTCD) is defined as the follows:

- Population: patients with previously untreated extensive-stage small cell lung cancer without presence or history of brain metastases at baseline
- Variable: Time from randomization until the first confirmed clinically meaningful deterioration on physical functioning and GHS/QoL EORTC QLQ-C30 select scales; confirmed clinically meaningful deterioration is defined as a clinically meaningful decrease from baseline that must be held for at least two consecutive assessments or an initial clinically meaningful decrease from baseline followed by death from any cause within 3 weeks.
- Treatments:
 - Experimental: tiragolumab + atezolizumab + CE (induction phase; four 21-day cycles) followed by tiragolumab + atezolizumab (maintenance phase; 21-day cycles)
 - Control: placebo + atezolizumab + CE (induction phase; four 21-day cycles) followed by placebo + atezolizumab (maintenance phase; 21-day cycles)
- Intercurrent events:
 - Start of NPT prior to a confirmed clinical meaningful deterioration
 - Early discontinuation from study treatment for any reason prior to a confirmed clinical meaningful deterioration
 - Death that occurs before patients report any clinically meaningful deterioration
- Handling of intercurrent events: A treatment policy strategy with regards to the start of NPT and early discontinuation; and while-on-treatment/while-alive strategy for death will be applied for the TTCD analysis.
- Summary measure: Hazard Ratio for TTCD

An alternative estimand for TTCD is defined similarly as above with the exception of the following:

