- Population: patients with previously untreated extensive-stage small cell lung cancer

For patients who discontinue study treatment for radiographic disease progression per RECIST v1.1 and enter the survival follow-up, the questionnaires will be completed at 3 months (± 30 days) and 6 months (± 30 days) following the visit in which progressive disease was confirmed. Patients who have not experienced a confirmed clinically meaningful deterioration by the clinical cutoff date will be censored at the last time when they completed an assessment. Patients with no baseline or post-baseline assessment will be censored at the date of randomization. According to the while on treatment/while-

alive strategy, patients who died before reporting any clinical meaningful deterioration will be censored at the last time when they completed an assessment. TTCD will be analyzed using the same methods as for the co-primary endpoint of PFS.

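### No visible section adjusts the TTCD hazard ratio for the baseline score that defines the event; an ordinary 4-point chance imbalance could shift it by roughly 0–25%, depending on inputs the documents do not give

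*SAP*

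**What the plan says.** SAP 1.1.1 (Table 2) and 5.4.2.3 define the event against the patient's own starting score: "confirmed clinically meaningful deterioration is defined as a clinically meaningful decrease from baseline that must be held for at least two consecutive assessments". A first such drop followed by death within 3 weeks also counts. The threshold is in SAP 5.4.2.3: "A score change of at least 10-point in GHS/QoL and functional subscale score is perceived by patients as clinically meaningful". The two scales are physical functioning and global health status (GHS), each rescaled to 0–100.

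For the analysis, SAP 5.4.2.3 states that "TTCD will be analyzed using the same methods as for the co-primary endpoint of PFS", and Protocol 6.4.2.4 agrees: "TTCD using the EORTC scale will be analyzed using the same methods as for PFS". Those methods are in Protocol 6.4 and 6.4.1. On the test, "PFS and OS will be compared between treatment arms with use of the unstratified log-rank test". On which version leads, "Unstratified analysis will be considered as primary results given the potential small sample size within each stratum". The hazard ratio comes from Cox models fitted with and without stratification. The stratified version uses the randomization factors, ECOG performance status and LDH (Protocol 6.4; SAP 5.3.4).

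No visible section enters the baseline QLQ-C30 score in a model or plans a sensitivity analysis on it. The text of SAP 5.3.2 (main analytical approach) and 5.5.1 (patient-reported outcomes) is not visible, and Protocol 6.4.1 contains a redacted block. The absence can therefore be stated only for the visible text.

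**The concern.** A confirmed fall of 10 points is easier to record from a high start than from a low one. High scorers have room to fall and tend to regress toward the mean; patients near the floor have little or no room. The chance of an event thus depends on the baseline score even without any treatment effect. In a trial of this size the arms can easily differ by a few points in mean baseline, and the arm that starts higher will then tend to show faster deterioration.

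What is at stake is the reading of the point estimate. The trial tests nothing formally, and SAP section 2 says that its emphasis is consistency with the global study, so readers will look at the hazard ratio itself. TTCD is also the only endpoint that SAP Table 1 visibly lists for the quality-of-life objective.

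**Working it through.** **1. Sample size.** Protocol 6.1 gives about 128 randomized and 15% with brain metastases. The primary-analysis-set target is redacted, so 128 cannot be reproduced exactly, but 108/0.85 = 127.1 and 109/0.85 = 128.2 are both consistent with it. Taking 128 × 0.85 = 108.8, the set is about 109 patients, or 54 per arm. The documents state no TTCD event count, score SD or power.

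**2. Floor.** GHS uses items 29–30, each on a 7-point scale, so it moves in steps of 100/12 = 8.33. A drop of at least 10 needs two steps (16.7), and a patient at 0 or 8.3 cannot have a score-based event. Physical functioning has five 4-point items, so its step is 100/15 = 6.67 and a drop needs 13.3. The impossible group is small: with an assumed GHS mean of 58 and SD of 22, about 1.5% lie below 10 (normal approximation). Most of the dependence comes from regression to the mean and room to fall.

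**3. Size of a chance imbalance.** SE of the difference in mean baseline = SD × √(4/N). The SD is assumed.

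| SD | SE, N = 128 | P(difference ≥ 4) | SE, N = 109 | P(difference ≥ 4) |
|---|---|---|---|---|
| 15 | 2.65 | 13.1% | 2.87 | 16.4% |
| 20 | 3.54 | 25.8% | 3.83 | 29.6% |
| 22 | 3.89 | 30.4% | 4.21 | 34.3% |
| 25 | 4.42 | 36.5% | 4.79 | 40.4% |

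Four points is about one SE for an SD of 20–25 and less common for an SD of 15.

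**4. Shift in the hazard ratio for a 4-point difference.** Simulated under no treatment effect: a stable patient level plus visit noise, scores rounded to the QLQ-C30 grid, the protocol form schedule, and an event defined as a drop of at least 10 at two consecutive forms. The death route is not modelled. A grid of 864 settings (12,000 patients each) varied SD 18–25, reliability 0.3–0.8, mean 60 or 78, drift 0 to −4 points per 12 weeks, spread of individual slopes, and whether low scorers also decline faster. Hazard ratio per 4 baseline points, median (range):

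| Reliability | Baseline not otherwise prognostic | Low scorers decline faster (stronger setting) |
|---|---|---|
| 0.3 | 1.198 (1.153–1.268) | 1.159 (1.122–1.216) |
| 0.4 | 1.170 (1.120–1.256) | 1.120 (1.083–1.174) |
| 0.5 | 1.141 (1.101–1.208) | 1.087 (1.049–1.134) |
| 0.6 | 1.118 (1.075–1.195) | 1.057 (1.026–1.093) |
| 0.7 | 1.090 (1.054–1.158) | 1.023 (0.997–1.046) |
| 0.8 | 1.066 (1.026–1.114) | 0.978 (0.958–1.003) |

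The full range is 0.958 to 1.268, that is −4% to +27%.

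Whole trials of 128 patients (15 scenarios, 1,500 trials each), regressing the unadjusted log hazard ratio on the observed baseline difference, agree. The ratio per 4 points was 1.118 in the base case (SD 22, reliability 0.6), 1.05–1.13 with baseline not prognostic, and 1.01–1.09 when low scorers also decline faster.

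**5. With baseline score in the Cox model.** The ratio per 4 points becomes 0.98–1.02 across the same 15 scenarios. Precision is unchanged: in the base case the SD of the log hazard ratio is 0.304 unadjusted and 0.308 adjusted. Further runs with 54 per arm and the on-treatment form schedule, over both scales, gave adjusted ratios of 0.93–1.04; the over-correction arose where baseline was strongly prognostic and reliability was low.

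**6. Against sampling error.** SE of the log hazard ratio ≈ 2/√events. With 30–80 events (assumed), the SE is 0.365–0.224 and the 95% CI extends by a factor of 2.05–1.55 each way. A 12% shift, ln 1.12 = 0.113, is 0.31–0.51 SE; a 25% shift, ln 1.25 = 0.223, is 0.61–1.00 SE.

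**The case against.** The strongest reply is that chance imbalance in any prognostic covariate is already part of the sampling error of a randomized comparison, so the confidence interval covers it. That is correct. A reader might infer that the planned hazard ratio is biased; randomization and blinding rule out that reading, and adjustment does not even narrow the spread of the estimate.

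A reader might also fix on a definite size. Taking GHS with SD 22, between-form correlation 0.4–0.7 and baseline not otherwise prognostic gives about 11–19% per 4 points. The documents supply none of those inputs. Only 38% of the settings in the grid fall in that band and 54% fall below it. If low scorers are sicker and decline faster, the two effects partly cancel. Stratifying randomization by ECOG status may also partly balance physical functioning.

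Other parts also stand. TTCD is labelled supportive, nothing is formally tested, and Protocol 6.4.2.4 plans score summaries at each timepoint, so an imbalance would be seen. An adjusted hazard ratio is conditional on baseline and may not match what the global study reports.

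This does not remove the point. Once an imbalance is visible, the unadjusted estimate is shifted in a largely predictable direction, and an adjustment chosen at that stage would look selective. Comparability is kept by reporting both estimates.

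**Conclusion.** The point holds as a minor one. The event is defined by the patient's own baseline score, and no visible section adjusts for that score. Given a 4-point difference in mean baseline, which is ordinary at this sample size if the SD is 20–25, the unadjusted hazard ratio shifts by roughly 0–25%, about 10–15% in mid-range cases. In nearly all settings the arm that starts higher looks worse.

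The size rests on assumed SD, between-form reliability and decline of low scorers, and on simulations that leave out the death route. It is a shift conditional on the observed imbalance and lies within the sampling error. Adjustment largely removes that dependence and leaves the SD of the log hazard ratio about the same.

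**What to change.** In SAP 5.4.2.3, with a matching line in Table 2, pre-specify for each scale a Cox model with treatment and that scale's continuous baseline score, reported alongside the planned unadjusted hazard ratio. At minimum, name it as a sensitivity analysis. Add baseline physical functioning and GHS scores by arm to the comparability summaries in SAP 5.7.2, whose listed examples do not include them.

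The cost is one covariate, already collected, and a sentence or two. No follow-up is lost, because SAP 5.4.2.3 already censors patients without a baseline assessment at randomization. The downside is that the adjusted hazard ratio is conditional on baseline, so the unadjusted one should stay for comparison with the global study.

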1.2 STUDY DESIGN

[figure not shown]
This is a Phase III, randomized, double-blind, placebo-controlled multicenter study in China designed to evaluate the safety and efficacy of tiragolumab plus atezolizumab and CE compared with placebo plus atezolizumab and CE in patients with chemotherapy-naïve ES-SCLC.

Eligible patients are stratified by Eastern Cooperative Oncology Group (ECOG) Performance Status (0 vs. 1) and lactate dehydrogenase (LDH) (\leq upper limit of normal [ULN] vs. $>$ ULN), and will be randomized 1:1 to receive one of the following treatment regimens:

- Arm A: tiragolumab + atezolizumab + CE (induction phase; four 21-day cycles) followed by tiragolumab + atezolizumab (maintenance phase; 21-day cycles)
- Arm B: placebo + atezolizumab + CE (induction phase; four 21-day cycles) followed by placebo + atezolizumab (maintenance phase; 21-day cycles)

The study schema is shown in [Figure 1](#).

Figure 1 Study Schema

CE=carboplatin and etoposide; ECOG PS=Eastern Cooperative Oncology Group performance scale; ES-SCLC= extensive-stage small cell lung cancer ; FAS=full analysis set; LDH=lactate dehydrogenase; n=number of patients; PAS= primary analysis set; RECIST=Response Evaluation Criteria in Solid Tumors; ULN=upper limit of normal.

Following the induction phase, patients will continue maintenance therapy with either tiragolumab plus atezolizumab (Arm A) or placebo plus atezolizumab (Arm B).

Treatment will be continued until radiographic disease progression according to Response Evaluation Criteria in Solid Tumors (RECIST) version 1.1, or as long as patients are experiencing clinical benefit, as assessed by the investigator, in the absence of unacceptable toxicity or symptomatic deterioration attributed to disease progression after an integrated assessment of radiographic data, biopsy results (if available), and clinical status. Patients who meet the criteria for disease progression per Response Evaluation Criteria in Solid Tumors (RECIST) v1.1 will be permitted to continue study treatment (atezolizumab plus tiragolumab or atezolizumab plus placebo) if they meet all of the criteria specified in study protocol (see Protocol, Section 3.1.2) and provide written consent.

Patients will undergo tumor assessments at baseline and every 6 weeks (± 7 days) for 48 weeks following Cycle 1, Day 1, regardless of treatment dose delays. After completion of the Week 48 tumor assessment, tumor assessments will be required every 9 weeks (± 7 days) thereafter, regardless of treatment dose delays. Patients will undergo tumor assessments until radiographic disease progression per RECIST v1.1, withdrawal of consent, study termination by the Sponsor, or death, whichever occurs first. Patients who are treated beyond disease progression per RECIST v1.1 will undergo tumor assessments at the frequency described above until study treatment is discontinued. Patients who discontinue treatment for reasons other than radiographic disease progression per RECIST v1.1 (e.g., toxicity, symptomatic deterioration) will continue scheduled tumor assessments at the frequency described above until radiographic disease progression per RECIST v1.1, withdrawal of consent, study termination by the Sponsor, or death, whichever occurs first), regardless of whether the patient starts a new anti-cancer therapy.

